10.1.3 Additional Points to Consider for PTEs and AEs

An untoward finding generally may:

- Indicate a new diagnosis or unexpected worsening of a pre-existing condition. (Intermittent events for pre-existing conditions underlying disease should not be considered PTEs or AEs.)
- Necessitate therapeutic intervention.
- Require an invasive diagnostic procedure.
- Require discontinuation or a change in dose of study medication or a concomitant medication.
- Be considered unfavorable by the investigator for any reason.
- PTEs/AEs caused by a study procedure (e.g., a bruise after blood draw) should be recorded as a PTE/AE.

Diagnoses vs. signs and symptoms:

- Each event should be recorded to represent a single diagnosis. Accompanying signs (including abnormal laboratory values or ECG findings) or symptoms should NOT be recorded as additional AEs. If a diagnosis is unknown, sign(s) or symptom(s) should be recorded appropriately as a PTE(s) or as an AE(s).

Laboratory values and ECG findings:

- Changes in laboratory values or ECG parameters are only considered to be PTEs or AEs if they are judged to be clinically significant (i.e., if some action or intervention is required or if the investigator judges the change to be beyond the range of normal physiologic fluctuation).

A laboratory re-test and/or continued monitoring of an abnormal value are not considered an intervention. In addition, repeated or additional noninvasive testing for verification, evaluation, or monitoring of an abnormality is not considered an intervention.

- If abnormal laboratory values or ECG findings are the result of pathology for which there is an overall diagnosis (e.g., increased creatinine in renal failure), the diagnosis only should be reported appropriately as a PTE or as an AE.

Pre-existing conditions:

- Of pre-existing conditions (present at the time of signing of informed consent), events that are considered accompanying symptoms of MDD should NOT be recorded as concurrent medical conditions, PTEs, or AEs.
- Other pre-existing conditions are considered concurrent medical conditions and should NOT be recorded as PTEs or AEs. Baseline evaluations (e.g., laboratory tests, ECG, X-rays) should NOT be recorded as PTEs unless related to study procedures. However, if the subject experiences an abnormality (e.g., internal bleeding due to blood sampling) associated with the baseline evaluations, the abnormality should be recorded as a PTE and recorded on eCRF. If the subject experiences a worsening or complication of such a concurrent condition, the worsening or complication should be recorded appropriately as a PTE (worsening or complication occurs before start of study medication) or an AE (worsening or complication occurs after start of study medication). The investigator should ensure that the event term recorded captures the change in the condition (e.g., “worsening of hypertension”).
- If a subject has a pre-existing episodic condition (e.g., asthma, epilepsy) any occurrence of an episode should only be captured as a PTE/AE if the episodes become more frequent, serious or severe in nature, that is, the investigator should ensure that the AE term recorded captures the change in the condition from Baseline (e.g., “worsening of...”).
- If a subject has a degenerative concurrent condition (e.g., cataracts, rheumatoid arthritis), worsening of the condition should only be captured as a PTE/AE if occurring to a greater extent to that which would be expected. Again, the investigator should ensure that the AE term recorded captures the change in the condition (e.g., “worsening of...”).

Worsening of PTEs or AEs:

- If the subject experiences a worsening or complication of a PTE after starting administration of the study medication, the worsening or complication should be recorded appropriately as an AE. The investigator should ensure that the AE term recorded captures the change in the condition (e.g., “worsening of...”).
- If the subject experiences a worsening or complication of an AE after any change in study medication, the worsening or complication should be recorded as a new AE. The investigator should ensure that the AE term recorded captures the change in the condition (e.g., “worsening of...”).

Changes in severity of AEs /Serious PTEs:

- If the subject experiences changes in severity of an AE/serious PTE, the event should be captured once with the maximum severity recorded.

Preplanned surgeries or procedures:

- Preplanned procedures (surgeries or therapies) that were scheduled prior to signing of informed consent are not considered PTEs or AEs. However, if a preplanned procedures is performed early (e.g., as an emergency) due to a worsening of the pre-existing condition, the worsening of the condition should be captured appropriately as a PTE or an AE. Complications resulting from any planned surgery should be reported as AEs.

Elective surgeries or procedures:

- Elective procedures (e.g., cosmetic surgery) performed where there is no change in the subject's medical condition should not be recorded as PTEs or AEs, but should be documented in the subject's source documents. Complications resulting from an elective surgery should be reported as AEs.

Insufficient clinical response (lack of efficacy):

- Insufficient clinical response, efficacy, or pharmacologic action, should NOT be recorded as an AE. The investigator must make the distinction between exacerbation of pre-existing illness and lack of therapeutic efficacy.

Overdose:

- All cases of overdose with any medication, including the case without manifested side effects, are considered AEs and will be recorded on the AE page of the eCRF. In addition, cases of overdose will be reported as special interest AEs.

Suicidality events:

- A completed suicide is always captured as an SAE based on its fatal outcome. Furthermore, active suicidal behavior such as suicidal ideation with a specific plan and suicide attempt will also be collected as an SAE.
- Unless the event in question meets the definition of "serious," suicidal thoughts or suicidal ideation without a specific plan or action will be collected as a non-serious AE in accordance with the standard AE reporting requirements.
- A subject who presents with self-mutilation should be asked by the investigator to clarify whether the subject was attempting suicide. If the subject was attempting suicide, the behavior will be collected as an SAE, and the specific suicidal behavior (e.g., wrist cutting) will be recorded in the eCRF. If the subject was not attempting suicide, the behavior will be collected as a non-serious AE in accordance with the standard AE reporting requirements.

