8.1 Study Medication

8.1.1 Dosage Form, Manufacturing, Packaging, and Labeling

In this protocol, the term study medication refers to all or any of the drugs defined below.

Table 8.a Study Medication

Name	Active Substance	Dosage Form	Strength	Manufacture
Lu AA21004 tablet	1-[2-(2,4-dimethyl-phenyl sulfanyl)-phenyl]-piperazine, hydrobromide	Indistinguishable round biconvex tablets	10 mg or 20 mg	Takeda Pharmaceutical Company Limited
Placebo tablet	None		—	

The study medications are identical in appearance.

As for the study medications for the placebo lead-in period, 14 tablets of placebo are packaged in 1 press-through pack (PTP) sheet, and a single sheet is enclosed in an outer carton. The 1 outer carton (including 7 days' spare tablets) will be provided to each subject in the placebo lead-in period.

As for the study medications for the double-blind treatment period, 14 tablets of Lu AA21004 or placebo are packaged in 1 PTP sheet. For Week 1 in the double-blind treatment period, 1 sheet (including 7 days' spare tablets) is enclosed in an Inner Carton 1, and, for Weeks 2 to 8 in the double-blind treatment period, 5 sheets (including 21 days' spare tablets) are enclosed in an Inner Carton 2. Inner Cartons 1 and 2 are packed together in an outer carton. The 1 outer carton will be provided to each subject in the double-blind treatment period.

The outer carton is labeled with a note that the formulation therein is used for a clinical study and pertinent information of the name and quantity of the study medication, the sponsor's name and address, manufacturing number, and storage conditions.

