10.1.9 Start Date

The start date of AEs/PTEs will be determined based on the criteria described below.

AE/PTE	Start Date
Signs, symptoms, and diseases (diagnosis)	Date when the subject or the investigator first notices the sign or symptom of the AE
Asymptomatic disease	Date when a definite diagnosis is determined based on the results of diagnostic testing. Even if obsolete findings are indicated based on the test findings or the approximate time of onset can be estimated, the date when a definite diagnosis is made should be recorded.
Worsening of concurrent medical conditions or PTEs	Date when the subject or the investigator first notices worsening of the disease or symptom.
Normal in the initial assessment after signing of informed consent but abnormal in the subsequent assessment (for PTEs) Abnormal in the assessment after the start of the study medication (for AEs)	Date when the test is performed in which a clinically significant abnormal test value is observed
Abnormal in the initial assessment after signing of informed consent and has worsened in the subsequent assessment (for PTEs) Abnormal in the assessment at the start of the study medication and has worsened in the subsequent assessment (for AEs)	Date when the test is performed in which a medically significant elevation, reduction, increase or decrease in clinical laboratory test values is observed

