10.2 Procedures

10.2.1 Collection and Reporting of AEs

10.2.1.1 PTE and AE Collection Period

Collection of PTEs will commence from the time the subject signs the informed consent to participate in the study and continue until the subject is first administered study medication in the

placebo lead-in period. For subjects who discontinue prior to the first study medication administration in the placebo lead-in period, PTEs are collected until the subject discontinues study participation.

Collection of AEs will commence from the time that the subject is first administered study medication in the placebo lead-in period. Routine collection of AEs will continue until Visit 8 or Early Termination Visit.

Collection of SAEs or special interest AEs will continue until the end of the follow-up period.

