13.1.5 Safety Analysis

AEs

The definition of treatment-emergent adverse events (TEAE) will be described in the statistical analysis plan (SAP). TEAEs will be summarized using the safety analysis set. TEAEs will be coded using the MedDRA and will be summarized by system organ class (SOC) and preferred term (PT). No statistical testing or inferential statistics will be generated.

A subject who has developed a same TEAE more than once will be counted as 1 subject in the severity category corresponding to the maximum severity of the event.

Clinical Laboratory Test, Weight, Vital Signs, and ECG

Summary statistics of observed values and changes at each time point (values at each time point in the double-blind treatment period – baseline) will be calculated for clinical laboratory tests, vital signs, ECG parameters, and weight for each treatment group. Incidences of values that are outside normal ranges and are potentially and clinically significant will be calculated.

C-SSRS

Descriptive statistics of C-SSRS will be calculated at each time point for each treatment group.

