1.2 Demographics and Other Baseline Characteristics	13
1.2.1 Summary of Demographics and Other Baseline Characteristics	13
1.2.2 Medical History and Concurrent Medical Conditions	15
1.2.3 Medication History and Concomitant Medications	16
1.3 Treatment Compliance.....	16
1.3.1 Study Drug Exposure and Compliance.....	16
2 Efficacy Analysis.....	17
2.1 Primary Endpoint(s) and Analytical Methods.....	17
2.1.1 Primary Analysis.....	17
2.1.2 Secondary Analysis (1).....	18
2.1.3 Secondary Analysis (2).....	18
2.2 Secondary Endpoint(s) and Analytical Methods.....	19
2.3 Other Analysis/Additional Endpoint(s) and Analytical Methods	22
2.4 Statistical/Analytical Issues	31
2.4.1 Adjustments for Covariates.....	31
2.4.2 Handling of Dropouts or Missing Data.....	31
2.4.3 Interim Analyses and Data Monitoring.....	31
2.4.4 Multicenter Studies	31
2.4.5 Multiple Comparison/Multiplicity	31
2.4.6 Use of an “Efficacy Subset” of Subjects.....	32
2.4.7 Active-Control Studies Intended to Show Equivalence or Non-Inferiority	32
2.4.8 Examination of Subgroups.....	32
3 Safety Analysis	33
3.1 Treatment-Emergent Adverse Event.....	33
3.1.1 Overview of Treatment-Emergent Adverse Events	33

3.1.2 Displays of Treatment-Emergent Adverse Events.....	34
3.2 Pretreatment Events and Placebo Lead-in Adverse Events	35
3.2.1 Displays of Pretreatment Events.....	35
3.2.2 Displays of Placebo Lead-in Adverse Events	36
3.3 Laboratory and Other Safety Data	37
3.3.1 Laboratory Test Results	37
3.3.2 Vital Signs, Physical Findings and Other Observations Related to Safety.....	38
4 Significance Level and Confidence Coefficient	44
Amendment History (Version Management).....	45
[Appendix 1] Change Comparison Table for Lu AA21004/CCT-004	1
[Appendix 2]Definition of PCS Criteria	1

Glossary

- Treatment-emergent adverse event (TEAE): An adverse event which occurs on or after the start of double-blind study drug
- Placebo lead-in adverse event: An adverse event which occurs on or after the start of placebo lead-in study drug before the start of double-blind study drug
- Drug-related adverse event: An adverse event that is considered to be either probable, or possible related to the double-blind study drug will be treated as related.
- Descriptive statistics: number of subjects, mean, standard deviation, maximum, minimum, and quartiles
- PCS: Potentially Clinically Significant

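### Protocol 10.1.3 does not say whether starting double-blind drug is a change in study medication, so under the SAP's occurrence-only definition a lead-in AE that worsens may or may not count as a TEAE

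*Protocol*

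**What the plan says.** Two neighbouring rules in Protocol 10.1.3 deal with an AE that gets worse.

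- Under worsening, the rule covers a subject who has a "worsening or complication of an AE after any change in study medication, the worsening or complication should be recorded as a new AE".
- Under changes in severity: "If the subject experiences changes in severity of an AE/serious PTE, the event should be captured once with the maximum severity recorded".

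The first rule has a condition and the second has none. The section does not say which prevails. Protocol 8.1.1 states "In this protocol, the term study medication refers to all or any of the drugs defined below", and its table lists both active and placebo tablets. What counts as a change is not defined there or elsewhere in the protocol.

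AEs can exist before randomized treatment begins: "Collection of AEs will commence from the time that the subject is first administered study medication in the placebo lead-in period" (10.2.1.1). Under 10.1.9 a symptomatic event is dated from when the sign or symptom is first noticed. The row for worsened conditions is labelled "Worsening of concurrent medical conditions or PTEs" and does not name AEs; a separate row covers test values that worsen, including for AEs.

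Protocol 13.1.5 leaves the TEAE definition to the SAP. The SAP glossary gives it as "An adverse event which occurs on or after the start of double-blind study drug", and a placebo lead-in adverse event as "An adverse event which occurs on or after the start of placebo lead-in study drug before the start of double-blind study drug". Neither entry mentions worsening. SAP 3.1.1 and 3.1.2 tabulate TEAEs by treatment group. SAP 3.2.2 tabulates lead-in AEs (all and serious) by SOC and PT for everyone who took lead-in drug, and specifies no split by treatment group or intensity.

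**The concern.** An AE can begin during the placebo lead-in and become more severe once randomized drug starts. Between-arm safety tables should catch that course. Whether they do depends on which of the two recording rules the site follows, and the protocol does not tell it.

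The between-arm AE comparison rests on the TEAE tables. Safety and tolerability is a secondary objective, and no data safety monitoring committee is used (Protocol 11.0). If active drug aggravates existing complaints, the events left out would fall mainly in the active arms, and the tables would understate the difference from placebo. The outputs could also disagree with each other. A subject who stops drug because a lead-in AE worsened would appear as an AE discontinuation in SAP 1.1.5, but not among the TEAEs leading to discontinuation in SAP 3.1.1 and 3.1.2.

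**Working it through.** The plan gives no figure on this point, so there is none to reproduce. The check follows one event through the text.

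**Step 1: one event, two records.** Take an AE that is mild from Study Day -4 and severe from Study Day 5 (days chosen for illustration).

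| | New-record rule applied | Single-record rule applied |
|---|---|---|
| Records | Two: Day -4 mild, Day 5 severe | One: severe |
| Start date of the severe record | Day 5 | Day -4 (first notice, 10.1.9) |
| SAP class of the severe record | TEAE | Placebo lead-in AE |
| Count in SAP 3.1.1 and 3.1.2 | 1, severe, onset interval Days 1 to 7 | 0 |
| Count in SAP 3.2.2 | 1 (the Day -4 record) | 1 |

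The same clinical course gives 1 or 0 TEAEs.

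**Step 2: which rule applies?** The rules fit together if the first is read as the special case (new record after a change in study medication) and the second as the default (one record otherwise). The event above is then a TEAE only if the first double-blind dose is a change in study medication. The protocol does not say so. A site could decide that it is, because the lead-in and double-blind supplies are described separately in 8.1.1. A site could also decide that it is not, because study medication covers all the tablets and the action categories in 10.1.12 contain no dose change.

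**Step 3: could the analyst repair it?** Protocol 10.2.1.2 lists the items documented per event. They include start and stop dates and severity, but no date of a change in severity. From a single record the analyst cannot tell whether the maximum was reached before or after Day 1, so a worsening clause in the SAP alone would not recover events already captured once.

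**Step 4: comparison case.** An AE that starts after the first double-blind dose is a TEAE under both rules. The problem is confined to AEs that start in the lead-in, are still present at Day 1, and then worsen.

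**Step 5: size.** Subjects affected per arm = 160 × P(lead-in AE) × P(ongoing at Day 1) × P(worsens). Only the 160 comes from the documents. With assumed probabilities:

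- low: 160 × 0.10 × 0.30 × 0.10 = 0.48
- high: 160 × 0.25 × 0.50 × 0.30 = 6.0

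This range shows only how the product behaves and is not an estimate for this trial.

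**The case against.** The strongest reply is that the conflict disappears on a sensible reading. The new-record rule is specific and the single-record rule general. In a fixed-dose trial, apart from stopping drug, the only changes the first rule can mean are the planned transitions. The rule just before it is parallel: a PTE that worsens after study medication starts becomes an AE. If worsening is handled at recording in this way, a SAP definition by occurrence is enough. Data handling rules and a data management plan also exist that are not among the documents, and they may settle the matter. C-SSRS, laboratory, vital-sign and ECG displays do not depend on AE start dates.

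Most of this stands. It shows that the loss is avoidable and that some safety signals have another route into the report. It does not show that sites will read the rules this way: the trigger is undefined, no precedence is given, and the second rule is written without exception. The unseen documents cannot be credited or faulted.

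Two stronger readings are tempting and should not be made.

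- A reader might infer that a blinded site cannot apply the new-record rule, because the tablet's content changes at the start of double-blind treatment only in the active arms. The documents do not support this. The lead-in is single-blind, and Inner Carton 1 is dispensed at Visit 3 and Inner Carton 2 from Visit 4 for every subject. The transitions are visible in all arms and can serve as the trigger.
- A reader might infer that the step from 10 to 20 mg is seriously obscured. An AE that starts on double-blind drug is a TEAE under either rule. Only the number of event records and the onset interval in the over-time table of SAP 3.1.2 could differ, and that table is descriptive.

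**Conclusion.** The point holds in a limited form. A recording rule with an undefined trigger, a second rule with no exception, and an occurrence-only TEAE definition together allow a lead-in AE that worsens on randomized drug to be left out of SAP 3.1.1 and 3.1.2. No one of these is sufficient alone. It would go too far to say that such AEs necessarily drop out of the TEAE tables: a site that treats the first double-blind dose as a change in study medication will record a new AE, and it will be counted.

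No number of affected subjects can be derived, because the documents give no lead-in AE rate. With a lead-in of about one week the number is probably small. The direction toward understating harm assumes that active drug worsens existing complaints and that at least some sites keep a single record. The reason to act is that the lost information may not be recoverable from the listed AE data, while the correction is nearly free and does no harm on either reading.

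**What to change.** 1. In Protocol 10.1.3, reconcile the two rules. State that the first double-blind dose counts, in all arms, as a change in study medication, and that the single-record rule applies only when no such change intervenes.
2. In the SAP glossary, define a TEAE as an AE that starts, or worsens in severity, on or after the first double-blind dose.
3. If data are already collected, query under the blind every lead-in AE that was ongoing at Day 1, asking whether it later worsened or led to drug withdrawal, and classify it accordingly. Protocol 13.1 places the blinded data review before unblinding. SAP 2.4.1 reports a decision already taken after that review, so this may have to be a supplementary query, still before the code is opened.

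The cost is a sentence or two in 10.1.3, one clause in the SAP and a short query list. The downside is a few more AE records and slightly higher TEAE counts.

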4.1.3 Japanese Phase II/III Clinical Studies

In Japan, 2 placebo-controlled, short-term studies (Study CCT-002 [multinational study] and Study CCT-003 [Japan local study]) were conducted in subjects with MDD. In addition, a long-term extension study (Study OCT-001) was conducted in those who completed Study CCT-003.

Study CCT-002 was conducted in 14 countries including Japan, Europe and the Asia Pacific region to evaluate the efficacy and safety of Lu AA21004 at doses of 5, 10 and 20 mg/day. For the mean changes from baseline in the MADRS total score at Week 8 (last observation carried forward [LOCF]) in the primary efficacy analysis (analysis of covariance [ANCOVA]), the mean differences of the Lu AA21004 5, 10 and 20 mg group compared to the placebo group were -0.61 (p = 0.91), -1.69 (p = 0.30) and -1.82 (p = 0.24), respectively. In addition, in the same analysis for Japanese population, the mean differences of the Lu AA21004 5, 10 and 20 mg group compared to the placebo group were 0.89, -2.74 and -3.45, respectively.

In Study CCT-002, Most TEAEs were mild or moderate, and TEAEs reported in more than 5% of subjects in any Lu AA21004 groups were nausea, nasopharyngitis, headache, dizziness, constipation, dry mouth, and insomnia. Of these, TEAEs with higher (≥ 2 -fold) incidence in any Lu AA21004 groups than that in placebo group were nausea, constipation, dry mouth, dizziness and insomnia.

In Study CCT-003, the efficacy and safety of Lu AA21004 at doses of 5 and 10 mg/day were evaluated in Japanese subjects with MDD. For the mean changes from baseline in the MADRS total score at Week 8 (LOCF) in the primary efficacy analysis (ANCOVA), the mean differences of the Lu AA21004 5 and 10 mg group compared to the placebo group were -2.03 (p = 0.10) and -1.04 (p = 0.40), respectively.

In Study CCT-003, TEAEs reported in more than 5% of subjects in any Lu AA21004 groups were nausea, diarrhoea, nasopharyngitis, somnolence, headache, and suicidal ideation. Of these, TEAEs with higher (≥ 2 -fold) incidence in the Lu AA21004 groups than that in the placebo group were nausea and suicidal ideation. For suicidal ideation, the incidence in the 10 mg group (8 subjects; 6.6%) was higher than in the placebo group (2 subjects; 1.6%) and 5 mg group (1 subject; 0.8%). In general, most TEAEs were mild or moderate, suggesting that there were no significant safety concerns about Lu AA21004.

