10.1.4 SAEs

An SAE is defined as any untoward medical occurrence that at any dose:

CONFIDENTIAL

1. Results in DEATH.
2. Is LIFE THREATENING.*
3. Requires inpatient HOSPITALIZATION or prolongation of existing hospitalization.
4. Results in persistent or significant DISABILITY/INCAPACITY.
5. Leads to a CONGENITAL ANOMALY/BIRTH DEFECT.
6. Is an IMPORTANT MEDICAL EVENT that satisfies any of the following:
 - May require intervention to prevent items 1 through 5 above.
 - May expose the subject to danger, even though the event is not immediately life threatening or fatal or does not result in hospitalization.
 - Includes any event or synonym described in the Takeda Medically Significant AE List ([Table 10.a](#)).

* The term “life threatening” refers to an event in which the subject was at risk of death at the time of the event; it does not refer to an event that hypothetically might have caused death if it were more severe.

Table 10.a Takeda Medically Significant AE List

Term	
Acute respiratory failure/acute respiratory distress syndrome (ARDS)	Hepatic necrosis
Torsade de pointes / ventricular fibrillation / ventricular tachycardia	Acute liver failure
Malignant hypertension	Anaphylactic shock
Convulsive seizure (including seizure and epilepsy)	Acute renal failure
Agranulocytosis	Pulmonary hypertension
Aplastic anemia	Pulmonary fibrosis (including interstitial lung disease)
Toxic epidermal necrolysis/Stevens-Johnson syndrome	Neuroleptic malignant syndrome / malignant hyperthermia
	Spontaneous abortion / stillbirth and fetal death
	Confirmed or suspected transmission of infectious agent by a medicinal product
	Confirmed or suspected endotoxin shock

The following events are also to be considered SAEs.

- Completed suicide
- Active suicidal ideation
- Active suicidal behavior such as suicide attempt
- Self-injury with suicide attempt

PTEs that fulfill 1 or more of the serious criteria above are also to be considered SAEs and should be reported and followed up in the same manner (see Sections [10.2.2](#) and [10.3](#)).

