3.3.2.3 Columbia-Suicide Severity Rating Scale (C-SSRS)

Analysis Set: Safety Analysis Set
 Analysis SUICIDAL IDEATION
 Variable(s): Wish to be Dead [Yes, No]

Non-Specific Active Suicidal Thoughts	[Yes, No]
Active Suicidal Ideation with Any Methods (Not Plan) without Intent to Act	[Yes, No]
Active Suicidal Ideation with Some Intent to Act, without Specific Plan	[Yes, No]
Active Suicidal Ideation with Specific Plan and Intent	[Yes, No]
INTENSITY OF IDEATION	
Most Severe Ideation	[Wish to be dead, Non-specific active suicidal thoughts, Active suicidal ideation with any methods (not plan) without intent to act, Active suicidal ideation with some intent to act, without specific plan, Active suicidal ideation with specific plan and intent]
Frequency	[Less than once a week, Once a week, 2-5 times a week, Every day/almost every day, Several times every day]
Duration	[Several seconds to several minutes/For a moment, Less than 1 hour/For a while, 1-4 hours/For a considerable time, 4-8 hours/Almost all hours of the day, More than 8 hours/Persistent or continuous]
Controllability	[Easy to control, A bit difficult but can control, Somewhat difficult but can control, Relatively difficult but can control, Cannot control, No intention to control]

Deterrents	[Desisted to commit suicide due to deterrent(s), Probably desisted to commit suicide due to deterrent(s), Cannot tell if I desisted to commit suicide due to deterrent(s), Probably did not desist to commit suicide due to deterrent(s), Did not desist to commit suicide due to deterrent(s), Not applicable]
Reasons for Suicidal Ideation	[Only to attract someone's attention, revenge, or gain a response, Almost to attract someone's attention, revenge, or gain a response, Fifty-fifty to attract someone's attention, revenge, or gain a response and end pain, Almost to end pain (could not live to put up with the pain and feelings), Only to end pain (could not live while putting up with the pain and feelings), Not applicable]

SUICIDAL BEHAVIOR

Actual Attempt	[Yes, No]
Non-Suicidal Self-Injurious Behavior	[Yes, No]
Interrupted Attempt	[Yes, No]
Aborted Attempt	[Yes, No]
Preparatory Acts or Behavior	[Yes, No]
Suicidal Behavior	[Yes, No]
Completed Suicide (other than screening)	[Yes, No]

Answer for Actual Attempts Only

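### Protocol 10.1.3 and 10.1.4 set different thresholds for serious suicidal ideation, so active ideation without a specific plan may be coded differently across sites

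*Protocol*

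**What the plan says.** Protocol 10.1.3, under suicidality events, divides ideation by whether there is a plan. On one side, "active suicidal behavior such as suicidal ideation with a specific plan and suicide attempt will also be collected as an SAE". On the other, "suicidal thoughts or suicidal ideation without a specific plan or action will be collected as a non-serious AE". The second sentence opens with a condition: "Unless the event in question meets the definition of" serious.

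Protocol 10.1.4 first gives a numbered definition, beginning "An SAE is defined as any untoward medical occurrence that at any dose", whose six items do not name ideation. After the table of medically significant events comes a further list of events that also count as SAEs. It includes "Active suicidal ideation", with no mention of plan or intent. Neither section defines active.

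The trial's own instrument records active ideation that stops short of a plan. SAP 3.3.2.3 has, for example, the category "Active Suicidal Ideation with Some Intent to Act, without Specific Plan".

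On collection, Protocol 10.2.1.1 ends routine AE collection at Visit 8 or Early Termination, and then says: "Collection of SAEs or special interest AEs will continue until the end of the follow-up period". The special interest events in 10.1.5 are skin reaction, allergic reaction, hepatic impairment and overdose; suicidal ideation is not among them.

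**The concern.** One section separates serious from non-serious ideation by the presence of a plan, the other by whether the ideation is active. Ideation that is active but has no plan falls between the two lines. A site that works from the explicit plan rule can code it non-serious, and a site that works from the SAE list will code it serious.

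Three things depend on that code:

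- the site's report to the sponsor, due in principle within 1 business day for an SAE (10.2.2);
- entry in the serious-TEAE summaries by treatment group (SAP 3.1.1 and 3.1.2);
- collection of a new event in the 4 weeks after the treatment period.

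The term matters in this programme. Protocol 4.1.3 names suicidal ideation as one of two TEAEs in CCT-003 with at least twice the placebo incidence. Section 11.0 provides for no data safety monitoring committee, so consistent coding at site level carries more weight.

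**Working it through.** **Text comparison.** The plan states no figure on this point, so there is none to reproduce. The table sets the two sections against the five C-SSRS ideation levels in SAP 3.3.2.3. It takes active in the sense of the C-SSRS labels, which is an assumption because the protocol does not define the word.

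| C-SSRS ideation level | Plan rule in 10.1.3, before its exception | List in 10.1.4 |
|---|---|---|
| 1. Wish to be dead (passive) | Non-serious | Not listed |
| 2. Active thoughts, non-specific | Non-serious | SAE |
| 3. Active, method considered, no intent | Non-serious | SAE |
| 4. Active, some intent, no specific plan | Non-serious | SAE |
| 5. Active, with plan and intent | SAE | SAE |

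The sections agree at levels 1 and 5, and the overlap is levels 2 to 4. Two readings would bring the sections together, and they give different codes:

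- The exception in 10.1.3 imports the 10.1.4 list. Levels 2 to 4 are then SAEs, and the plan rule decides only passive thoughts.
- Active in 10.1.4 means what 10.1.3 suggests when it gives ideation with a specific plan as an example of active suicidal behaviour. Levels 2 to 4 are then non-serious unless a numbered criterion is met.

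**What is lost and what is not.**

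- *On treatment.* All TEAEs are tabulated whatever their seriousness (SAP 3.1.2). The C-SSRS is summarised at each visit to Week 8 and over the whole post-dose period (SAP 3.3.2.3 and 3.3.2.4). Only the serious-TEAE rows move.
- *Follow-up.* Protocol 9.3.6 assesses AEs continuing from Visit 8 or early termination, new SAEs, and special interest AEs. Appendix A schedules no C-SSRS at this contact. New-onset ideation at levels 2 to 4 is therefore collected if coded serious and not collected if coded non-serious, and no other scheduled assessment recovers it.
- *Tables.* The SAP glossary gives a TEAE a start but no end date, so follow-up events can enter the serious-TEAE tables.

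**Scale.** Inputs: CCT-003 ideation incidence of 6.6% (8 subjects) at 10 mg and 1.6% (2 subjects) on placebo (Protocol 4.1.3); 160 subjects per group (Protocol 13.3). Expected subjects with an ideation TEAE = 160 × rate:

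- 10 mg: 160 × 0.066 = 10.56, about 10.6
- placebo: 160 × 0.016 = 2.56, about 2.6

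The share that is active without a plan is not documented. Multiplying by an assumed share gives:

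| Assumed share | 0% | 25% | 50% | 75% | 100% |
|---|---|---|---|---|---|
| 10 mg | 0 | 2.6 | 5.3 | 7.9 | 10.6 |
| Placebo | 0 | 0.6 | 1.3 | 1.9 | 2.6 |

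These are on-treatment counts whose seriousness code could turn on the reading. They do not estimate the number of events missed in follow-up, for which the documents give no rate.

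**The case against.** A reader might infer that the two sections flatly contradict each other. The documents do not support that. The non-serious rule in 10.1.3 is conditional, and 10.1.4 refers to its serious criteria after its additional list has been given. Section 10.2.2 also points to 10.1.4 for the serious criteria. Together these favour the reading in which 10.1.4 governs, and the plan rule would still have work to do for passive thoughts. This part of the objection stands. It does not remove the problem, because the exception speaks of a definition while active ideation sits in a list placed after that definition, and active is left undefined. A site that applies the explicit plan rule is not being unreasonable.

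It is also fair to say that the consequences are partly covered. On-treatment ideation is counted elsewhere, and ideation continuing at Visit 8 is followed. Withdrawal for suicide risk runs on investigator judgement or MADRS item 10 (7.5.1), not on the SAE code. TEAE summaries are descriptive, with no testing (Protocol 13.1.5). Under double-blind allocation, inconsistent coding has no evident reason to favour one arm.

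Finally, the CCT-003 rates are a weak guide. The 5 mg group had 1 subject (0.8%), below placebo. CCT-002, which did test 20 mg, does not list ideation among its TEAEs above 5%. A significance test of the CCT-003 imbalance would add nothing, since the fault lies in the coding rule and does not depend on that comparison.

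**Conclusion.** The point holds as an unresolved ambiguity that is worth correcting. Two thresholds apply to active ideation without a specific plan, and the text does not say plainly which prevails. The firmest consequence is in follow-up: new-onset events of this kind after Visit 8 or Early Termination are collected under one reading and not under the other. The site's 1-business-day report and the serious-TEAE rows also turn on the code.

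The size is unknown. If the CCT-003 rates applied here, between 0 and about 10.6 subjects at 10 mg, and between 0 and about 2.6 on placebo, could have their code depend on the reading. A reader might carry that range over to the 20 mg arm, but CCT-003 tested only 5 and 10 mg. A reader might also infer that on-treatment ideation would go uncounted or that the arms would be compared with bias; the documents support neither. What they tie directly to the code is the site's notice to the sponsor. The sponsor's regulatory timelines in 10.3.1 are a separate step.

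The verdict assumes that active in 10.1.4 may be read in the C-SSRS sense, and that sites have no further guidance outside these documents.

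**What to change.** Reconcile 10.1.3 and 10.1.4 into one rule that defines active suicidal ideation, and have both sections cite it. Word it so that it can be applied to an event reported without a C-SSRS interview: 10.2.1.2 says that the scale is not a primary means of collecting AEs, and the follow-up contact may be by telephone. Which ideation counts as serious is for the sponsor's safety physicians to decide.

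Separately, collect new suicidal ideation and behaviour to the end of follow-up regardless of seriousness. This needs matching changes in 10.2.1.1, 9.3.6 and the follow-up note to Appendix A. The SAP should state how these follow-up events are displayed, since other non-serious AEs stop at Visit 8 or Early Termination.

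The cost is protocol wording, a note to sites, one sentence in the SAP, and a few more event forms at a contact that is already scheduled.
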